11.2. Sample Size Determination

Sample size calculations are performed under the following assumptions:

- immune response is measured by HI antibody titers against the four influenza vaccine strains
- a standard deviation of 2 at the \log_2 scale for HI antibody titers.

As four seasonal influenza strains will be assessed for which non-inferiority is to be shown, 94.6% power is required for each individual seasonal influenza strain to ensure an overall power of at least 80%. To have 94.6% power for an individual influenza strain, 86 evaluable subjects/group are required. If approximately 5% subjects are unevaluable (due to dropout, missing data, or seasonal influenza), 90 randomized subjects/arm will be needed.

This sample size ensures at least 80% power, assuming statistical independence between the HI antibody titers for the four seasonal influenza strains. As some correlation between the responses to the four strains is likely, the actual overall power may be higher.

11.3. Subject Information

For all subjects, demographic characteristics (eg, age, height, weight, body mass index [BMI], race, and gender), and other baseline characteristics (eg, physical examination, medical history, and concomitant diseases) will be tabulated and summarized with descriptive statistics.

11.4. Immunogenicity Analyses

The **primary immunogenicity objective** is to demonstrate the non-inferiority of the concomitant administration of Ad26.RSV.preF and seasonal influenza vaccine versus the administration of seasonal influenza vaccine alone in terms of humoral immune response expressed by the GMTs of HI antibody titers against all four influenza vaccine strains 28 days after the administration of influenza vaccine, using a non-inferiority margin of 2 for the GMT ratio (Control group/CoAd group).

The primary immunogenicity objective will be assessed by calculating the 95% one-sided upper confidence limit for the difference in log-transformed HI antibody titers for each of the four seasonal influenza vaccine strains between Control and CoAd groups. The confidence limit will be calculated using Welch's t-interval method. The confidence limit will be back-transformed (by exponentiation) to a GMT ratio and compared to the non-inferiority limit of 2.

Only if the 95% one-sided upper confidence limit for the GMT ratio (Control group/CoAd group) of the HI antibody titers lies below 2 for each of the four vaccine strains, non-inferiority of co-administration versus separate administration will be concluded. If one or more confidence limits for the GMT ratio exceed 2, non-inferiority cannot be concluded.

As a sensitivity analysis, the primary endpoint will also be evaluated adjusting for baseline HI levels.

The **secondary and exploratory efficacy endpoints** are listed in Section [2.1](#).

Continuous secondary and exploratory variables will be summarized with descriptive statistics of the actual values and the changes from baseline where appropriate. Descriptive statistics (geometric mean and 95% confidence interval for ELISA, virus neutralization and HI assays; median and quartiles for ELISpot and intracellular cytokine staining [ICS]) will be calculated for continuous immunologic parameters at all timepoints. For the humoral assays, geometric mean

fold rises from baseline and corresponding 95% confidence intervals might additionally be calculated. For immunogenicity, baseline is considered as the last assessment pre-vaccination. Graphical representations of immunologic parameters will be made as applicable.

No formal non-inferiority assessments for the secondary immunological parameters for seasonal influenza and RSV will be performed, but upper confidence limits for GMT ratios, as described for the primary endpoint, may be calculated and assessed for relevance by comparison to the non-inferiority limit of 2 as used in the primary analysis.

Similarly, the difference in proportions of seroconverted and seroprotected subjects between Control and CoAd groups can be estimated together with the 95% one-sided confidence limit (calculated using Wilson's score method) and compared to a 10% non-inferiority limit. Note that the study is only powered for the four primary comparisons and does not have sufficient power to show non-inferiority of co-administration compared to control for all immunogenicity markers for seasonal influenza and RSV. Consequently, by chance the study may fail to show non-inferiority for one or more secondary endpoints even in the absence of interference between seasonal influenza and RSV vaccine administrations.

For categorical variables, frequency tables will be presented. Difference in proportions and corresponding confidence intervals may be calculated where appropriate.

The primary immunogenicity endpoint will be based on the PPII set. The analysis set for the secondary and exploratory immunogenicity responses related to influenza will be the PPII set, and those related to RSV will be the PPRI. As a sensitivity analysis, key tables may also be based on the FA set. Depending on their occurrence, the effect of natural infections might be further explored.

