Blood will be collected from all subjects to assess humoral immune responses pre-vaccination on each dosing day, and at 28 days after the second vaccination (or at the early exit visit if the subject prematurely terminates the study before Day 57 without withdrawing consent^a); cellular immune responses may be assessed at these timepoints in a subset containing 40 randomized subjects (ie, 20 per group).

^a Immunogenicity blood samples will only be taken if early exit is at least 14 days after the previous immunogenicity blood draw.

[figure not shown]
An independent unblinded statistician and unblinded biomarker representative will present data to the DRC if non-inferiority of the concomitant administration of influenza vaccine with Ad26.RSV.preF versus the administration of influenza vaccine alone is not demonstrated, based on the immunogenicity analysis at 28 days after the first dose. The DRC will decide if subjects should be offered repeat influenza immunization (see Section 11.6 for more details).

The study duration will be approximately 30 weeks per participant. The study comprises vaccination for each subject on Day 1 and Day 29, a 28-day follow-up period after each vaccination, and a follow-up until 6 months after the second vaccination. The end of the study will be the last subject's last visit by telephone at 6 months after the second vaccination.

If symptoms of an RTI develop from Day 1 through the end of the study, subjects should record signs and symptoms of the RTI using a specific RTI Symptoms Form and, if feasible, take a nasal turbinate sample. Details on procedures in the event of an RTI are described in Section 9.2.3.

Unscheduled study visits may be performed based on investigator's clinical judgment and may include further evaluations, as needed.

A diagram of the entire study design is provided in [Figure 1](#).

Figure 1: Schematic Overview of the Study

*by telephone

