9.1.4. Second Vaccination (Day 29)

Visit 3: Vaccination 2

Verification of selected eligibility criteria,^a abbreviated physical examination (at the discretion of the investigator) and measurement of vital signs will be performed for all subjects pre-vaccination. Pre-dose samples for baseline immunogenicity will be collected. Before vaccination, the investigator must check for any symptoms of an acute illness or body temperature ≥ 38.0 °C. In such a situation, the subject may be vaccinated up to, and no later than 10 days after the scheduled vaccination, or be withdrawn at the discretion of the investigator.

Administration of second dose of study vaccine according to [Table 4](#).

^a To include fever and any acute illness that precludes vaccination; also receipt of any routine immunizations.

Subjects will be closely observed for a minimum of 30 minutes post-vaccination to monitor for the development of any acute reactions, or longer if deemed necessary by the investigator. Any unsolicited, solicited local or systemic AEs and vital signs will be documented in the eCRF by study-site personnel following this observation period.

Subjects will be provided with a second subject diary, thermometer, and ruler to measure and record body temperature, solicited local and systemic AEs for 7 days post-vaccination. The subject diary for the first vaccination will be reviewed and collected.

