9.2. Study Evaluations

9.2.1. Immunogenicity

Venous blood samples of approximately 20 mL and 40 mL will be collected for the determination of humoral and cellular responses, respectively, pre-vaccination on each dosing day, as well as 28 days after the second vaccination, or at the early exit visit if the subject prematurely terminates the study, without withdrawing consent. (Blood samples for immunogenicity will only be collected if the early exit is at least 14 days after the previous immunogenicity blood draw). Sample collection and processing will be performed by the staff at the clinical site according to current versions of approved standard operating procedures.

It is assumed that all enrolled subjects will have a pre-existing immune response due to previous RSV exposure as well as influenza-specific responses to one or more strains, either by natural exposure to influenza or by annual influenza vaccination (not including the 2017/18 influenza season).

Humoral and cellular immunogenicity evaluations are summarized in [Table 5](#) and [Table 6](#), respectively. Humoral immune responses will be assessed in all subjects; cellular immune responses may be assessed in a subset containing 40 randomized subjects (ie, 20 per group).

Table 5: Summary of Immunogenicity Assays (Humoral)

Assay	Purpose
Primary endpoints	
HAI	Hemagglutination inhibition assay to influenza vaccine strains
Secondary endpoints	
RSV neutralization A2	Analysis of neutralizing antibodies to the A2 strain
F-protein antibody (ELISA; pre- and/or post-fusion)	Analysis of antibodies binding to RSV F protein in post-fusion and/or pre-fusion form
HAI	Hemagglutination inhibition assay to influenza vaccine strains
Exploratory endpoints	
RSV strain cross-neutralization	Analysis of cross-neutralizing antibodies to B and/or a different A strain
F-protein antibody specificity characterization	Analysis of RSV, pre-fusion and post-conformation specific antibodies, antibody binding to pre-F or post-F after adsorption with pre-F or post-F proteins, and epitope mapping
Adenovirus neutralization	Analysis of neutralizing antibodies to adenovirus
Functional and molecular antibody characterization	Analysis of antibody characteristics including ADCC, ADCP, avidity, Fc characteristics, Ig isotype

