11.6. Planned Analyses

- **28 days post-first dose immunogenicity analysis:** at 28 days post-first dose, an immunogenicity analysis will be performed by an independent unblinded statistician. The goal of this analysis will be to evaluate the non-inferiority of the concomitant administration of Ad26.RSV.preF and seasonal influenza vaccine versus the administration of seasonal influenza vaccine alone in terms of the humoral immune response expressed by the GMTs of HI antibody titers against the four influenza vaccine strains. The independent unblinded statistician and unblinded biomarker representative will present data to the DRC if non-inferiority of concomitant versus separate administration is not demonstrated. The DRC will decide if subjects should be offered repeat influenza immunization after Day 57. If non-inferiority is not demonstrated but the following criteria⁸ are fulfilled, subjects would not be revaccinated:
 - The lower bound of the 95% confidence interval for the percentage of subjects achieving seroconversion for HI antibody should meet or exceed 30%
 - The lower bound of the 95% confidence interval for the percentage of subjects achieving an HI antibody titer $\geq 1:40$ should meet or exceed 60%
- **Primary analysis:** 28 days post-second dose safety and immunogenicity analysis. This analysis will be performed based on unblinded data. The goal of this analysis will be to evaluate the primary objectives. The blind will be maintained at the subject/site level.

- **Final analysis:** 6 months post-second dose safety analysis. This analysis will be performed based on unblinded data. The goal of this analysis will be to assess safety.

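### The primary Welch test is valid and meets its stated power, but leaving the Day 1 HI titer to a sensitivity analysis probably gives up precision in a trial that must pass on all four strains

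*Protocol*

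**What the plan says.** Section 11.4, and the Synopsis in the same terms, computes for each of the four strains a one-sided 95% upper limit for the Control minus CoAd difference in mean log HI titer. It uses Welch's t-interval and back-transforms the limit to a GMT ratio. Non-inferiority is concluded only if all four limits lie below 2. Baseline then has one role: "As a sensitivity analysis, the primary endpoint will also be evaluated adjusting for baseline HI levels".

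The covariate is already planned. Section 3.1 states: "Blood will be collected from all subjects to assess humoral immune responses pre-vaccination on each dosing day". Section 9.2.1 assumes that enrolled subjects have pre-existing RSV immunity, "as well as influenza-specific responses to one or more strains, either by natural exposure to influenza or by annual influenza vaccination".

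Section 11.2 sizes the trial on an SD of 2 on the log2 scale, 94.6% power per strain and 86 evaluable subjects per group. It assumes independent strains for the 80% overall power and adds: "As some correlation between the responses to the four strains is likely, the actual overall power may be higher". It makes no allowance for baseline adjustment.

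On what baseline means, Section 11.4 says: "For immunogenicity, baseline is considered as the last assessment pre-vaccination". Section 9.1.4 says of the Day 29 visit: "Pre-dose samples for baseline immunogenicity will be collected".

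**The concern.** A pre-vaccination titer that predicts the post-vaccination titer removes variance from the group comparison at no sampling cost. Here the adjusted result will be computed but cannot decide non-inferiority, and the protocol gives no reason for that order.

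Precision per strain matters more than usual. The four tests form an all-or-nothing rule, so a shortfall on one strain defeats the objective, and planned four-strain power is only just above 80%. A false failure also has consequences: under Section 11.6 the unblinded results go to the DRC, which decides whether repeat influenza immunization should be offered.

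A minor side point is that the word baseline is used for both pre-dose samples. The Day 29 pre-dose sample carries the primary HI endpoint, so the covariate should be named by day.

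**Working it through.** **Inputs from the protocol.** One-sided alpha 0.05; margin 2, which is 1 on the log2 scale; SD 2 (log2); 86 evaluable per group; 1:1 allocation; all four strains must pass (11.2, 11.4, 3.1).

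**Inputs assumed.** True GMT ratio 1 (not stated, but it reproduces the planned 86); rho, the correlation of Day 1 with Day 29 log titer, from 0 to 0.5 and the same in each strain.

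**1. The plan's own figure.**
- SE = 2 × √(2/86) = 0.305; non-centrality = 1/0.305 = 3.279; df = 170.
- Power per strain, from the non-central t, is 0.9475. Four independent strains: 0.9475⁴ = 0.806.
- With 85 per group the power is 0.9454, below 0.946, so 86 is the smallest adequate size. The stated figures reproduce.

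**2. What adjustment does in principle.** The residual SD becomes 2 × √(1 − rho²). At rho 0.5 this is 2 × √0.75 = 1.732, giving SE = 1.732 × √(2/86) = 0.264 and non-centrality 3.786. With df 169 the power is 0.9832 per strain, and 0.9832⁴ = 0.935. This is slightly optimistic, because it ignores the cost of estimating the slope and of a robust standard error.

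**3. Simulation with those costs included.** y = 2 × (rho·x + √(1 − rho²)·e), slope estimated in each trial, t with 169 df, 600,000 trials per rho (Monte Carlo SE about 0.1 point on four-strain power). Four-strain power is the fourth power of the per-strain value. The Welch reference is 80.6%.

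| rho | HC3 per strain | HC3 four strains | Change, points | HC2 four strains |
|---|---|---|---|---|
| 0 | 94.46% | 79.6% | -1.0 | 80.2% |
| 0.1 | 94.63% | 80.2% | -0.4 | 80.7% |
| 0.2 | 95.19% | 82.1% | +1.5 | 82.6% |
| 0.3 | 96.03% | 85.0% | +4.4 | 85.5% |
| 0.5 | 98.21% | 93.0% | +12.4 | 93.3% |

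Break-even is near rho 0.12 for HC3 and 0.09 for HC2.

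**4. Correlated strains.** With an assumed between-strain correlation of 0.5 in both Day 1 titers and residuals (200,000 four-strain trials per rho), Welch has 84.9%. HC3 has 84.1, 84.6, 86.0, 88.2 and 94.3% at the same values of rho, a change of -0.8, -0.3, +1.1, +3.3 and +9.4 points.

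**5. Type I error at a true ratio of 2.** At rho 0, 0.3 and 0.5, with group SDs 2/2, 1.5/2.5 and 2.5/1.5 (100,000 trials each): HC3 4.8–4.9%, HC2 4.9–5.1%, Welch 4.9–5.1%. All hold the nominal 5%.

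**6. If the planning assumptions slip** (formula of step 2, independent strains):

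| Case | Unadjusted | Adjusted, rho 0.3 | Adjusted, rho 0.5 |
|---|---|---|---|
| True ratio 1.1, SD 2 | 59.8% | 66.9% | 80.1% |
| True ratio 1, SD 2.5 | 48.2% | 55.5% | 70.1% |

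**7. Discrete titers with an assay floor.** Simulated with such titers, the four-strain gain is still about 3 points at rho 0.3 and about 10 at rho 0.5.

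**The case against.** The case for leaving the plan alone is a fair one. The Welch test is prespecified, valid and meets its power target, and the adjusted analysis will be produced anyway; only which of the two decides is at issue. The benefit rests on a correlation that the protocol does not give. Section 9.2.1 assumes prior responses to at least one strain, not all four, and does not link them to the Day 29 titer. The largest gain needs rho 0.5 in every strain and independent strains, while Section 11.2 itself expects some correlation between strains. This is a Phase 2a trial, and failing non-inferiority does not by itself lead to revaccination, because Section 11.6 adds seroconversion and titer criteria. Changing the primary analysis also means an amendment.

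Most of this stands, and it limits the point to one of efficiency with an uncertain size. It does not remove it. The loss if rho is near zero is about 1 point or less, against roughly 3 to 4 points gained at rho 0.3 and 9 to 12 at rho 0.5. The worry that real HI titers are coarse and floored is answered by step 7.

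The objection on the word baseline largely succeeds. Influenza vaccine is given only on Day 1, Section 9.1.3 also calls the Day 1 sample baseline, and the Day 29 sample is a sensible RSV baseline in the Control group. Day 1 is the natural reading for HI. Naming it is tidying, and the main point does not depend on it.

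**Conclusion.** The point holds as a recommended improvement, not an error. From about rho 0.2 upward, a Day 1-adjusted primary analysis raises the chance of a correct four-strain conclusion: by 1.5, 4.4 and 12.4 points at rho 0.2, 0.3 and 0.5 with independent strains, or 1.1, 3.3 and 9.4 points with between-strain correlation 0.5. Below about rho 0.12 it gains nothing with HC3 and loses up to about 1 point. These figures assume SD 2, a true ratio of 1, 86 per group and one value of rho for all strains; rho may in fact differ by strain. The estimand does not change: under randomization, linear adjustment on the log scale targets the same GMT ratio. Confidence is medium, because the size depends on a correlation that the protocol does not supply.

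**What to change.** Before the analysis described in Section 11.6, where "at 28 days post-first dose, an immunogenicity analysis will be performed by an independent unblinded statistician", amend Section 11.4 and the Synopsis as follows:

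- Make the primary analysis, per strain, an ANCOVA of log2 Day 29 HI titer on group and log2 Day 1 HI titer, naming the Day 1 pre-vaccination sample instead of baseline.
- Name the heteroscedasticity-robust standard error: HC3, or HC2, which costs less at low rho.
- Keep the one-sided 95% upper limit for Control/CoAd, the margin of 2 and the all-four rule.
- Keep the unadjusted Welch interval as the sensitivity analysis.
- State a rule for subjects with no Day 1 titer.
- State which method applies to the secondary comparisons, where "upper confidence limits for GMT ratios, as described for the primary endpoint, may be calculated"; otherwise they would change method by reference.

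The cost is one amendment, which may need IEC/IRB approval before it is implemented (Section 17.1). No new samples or subjects are needed. If rho proves to be near zero, four-strain power falls by about 1.0 point with HC3 or 0.4 point with HC2.

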11.5. Safety Analyses

No formal statistical testing of safety data is planned. All safety data will be analyzed descriptively by regimen.

Adverse Events

The verbatim terms used in the eCRF by investigators to identify AEs will be coded using the Medical Dictionary for Regulatory Activities (MedDRA). All reported AEs with onset during the active phase (ie, AEs occurring after vaccination up to 28 days post-vaccination), and all SAEs will be included in the analysis. For each AE, the number and percentage of subjects who experience at least 1 occurrence of the given event will be summarized by group.

Summaries, listings, datasets, or subject narratives may be provided, as appropriate, for those subjects who die, who discontinue study vaccine due to an AE, or who experience a severe AE or an SAE.

Summaries and/or listings may be provided separately for AEs with onset outside the above defined timeframe (ie, beyond 28 days post-vaccination) and that were reported pre-dose at the moment of subsequent vaccinations for studies using multiple doses.

Solicited local (at the Ad26.RSV.preF [or placebo] and seasonal influenza vaccine injection sites) and systemic AEs will be summarized descriptively. The overall frequencies per vaccine group as well as frequencies according to severity and duration will be calculated for solicited AEs. In addition, the number and percentages of subjects with at least 1 solicited local (at injection site) or systemic AE will be presented. Frequencies of unsolicited AEs, separately for all and vaccination-related only, will be presented by System Organ Class and preferred term.

Vital Signs

A tabulation of the distribution of temperatures per half degree intervals will be provided. For systolic and diastolic blood pressures, pulse rate and respiratory rate, the percentage of subjects with values beyond clinically relevant limits will be summarized.

Electrocardiogram (ECG)

Any abnormalities in ECG parameters (at screening on Day 1) will be listed.

Physical Examination

Physical examination abnormalities will be reported as AEs, according to the investigator.

11.6. Planned Analyses

- **28 days post-first dose immunogenicity analysis:** at 28 days post-first dose, an immunogenicity analysis will be performed by an independent unblinded statistician. The goal of this analysis will be to evaluate the non-inferiority of the concomitant administration of Ad26.RSV.preF and seasonal influenza vaccine versus the administration of seasonal influenza vaccine alone in terms of the humoral immune response expressed by the GMTs of HI antibody titers against the four influenza vaccine strains. The independent unblinded statistician and unblinded biomarker representative will present data to the DRC if non-inferiority of concomitant versus separate administration is not demonstrated. The DRC will decide if subjects should be offered repeat influenza immunization after Day 57. If non-inferiority is not demonstrated but the following criteria⁸ are fulfilled, subjects would not be revaccinated:
 - The lower bound of the 95% confidence interval for the percentage of subjects achieving seroconversion for HI antibody should meet or exceed 30%
 - The lower bound of the 95% confidence interval for the percentage of subjects achieving an HI antibody titer $\geq 1:40$ should meet or exceed 60%
- **Primary analysis:** 28 days post-second dose safety and immunogenicity analysis. This analysis will be performed based on unblinded data. The goal of this analysis will be to evaluate the primary objectives. The blind will be maintained at the subject/site level.

- **Final analysis:** 6 months post-second dose safety analysis. This analysis will be performed based on unblinded data. The goal of this analysis will be to assess safety.

